Children identified as potential DD members who score less than 11 points on the ASD screen and have no indication of a previous ASD diagnosis or autism special education exceptionality will undergo a reduced data collection protocol in SEED 3 because of resource limitations and because a large sample of DD children in SEED 1 and SEED 2 underwent the full SEED protocol and we have already gleaned much valuable information on this group. Because the DD group is such an important source for case finding, they will not be eliminated in SEED 3; rather, those who score less than 11 points on the ASD screen and have no indication of a previous ASD diagnosis or autism special education exceptionality (and thus remain classified as DD rather than being re-classified as POSSIBLE ASD) will not undergo the most costly aspects of SEED data collection – the in person developmental assessment, biosample collection, or anthropometry measurements. They will still continue to be included in the more resource efficient data collection processes – the maternal interview and the self-administered forms included in a mailing that are focused on maternal, paternal, and child health. Thus, they will still contribute to many analyses, and be particularly helpful in assessing potential recall bias.

1. Final ASD

ASD case confirmation will be established by administering the Autism Diagnostic Interview (ADI-R, Appendix G.1) to the primary caregiver, and the appropriate module of the Autism Diagnostic Observation Schedule (ADOS, Appendix G.2) to the child. Results from previous administration of the ADOS, ADI-R, or Mullen will not be accepted in lieu of testing for SEED.

- An ASD case is defined as any child who receives a complete developmental evaluation and meets the cutoff for autism on the ADI-R and ASD on the ADOS (see Figures 6-8). Note: Final ASD cases might have originated from ASD, DD, or POP samples.
 - o To fall within the spectrum cutoff on the ADI-R, a child must have a social domain score ≥ 10 , communication score ≥ 7 (nonverbal subject) or communication score ≥ 8 (verbal subject), and behavior score ≥ 3 .

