 - o To fall within the spectrum cutoff on the ADOS, a child must have the minimum number of points as indicated on the most recent diagnostic algorithms (Gotham et al., 2007) according to the module administered, chronological age of the child, and language level of the child. For example, a child administered Module 1 who does not have any words must score 11 or more points in order to be considered within the ASD range.

ADOS cutoff scores to fall within the spectrum by module; ADOS WPS 2002; Gotham et al., 2007

	Minimum number of points for ASD classification
Module 1, no words	≥ 11
Module 1, some words	≥ 8
Module 2, younger than age 5	≥ 7
Module 2, aged 5 years or older	≥ 8
Module 3	≥ 7

If results are discordant on the ADI-R and ADOS, an algorithm was developed to determine final ASD status. The algorithm was developed by SEED epidemiologists, pediatricians, and psychologists who have extensive experience with evaluation and research involving children with ASD and was based on previous algorithms developed by the Collaborative Programs for Excellence in Autism, discussions with instrument authors, and an extensive review of the

[figure not shown]
literature. The algorithm states that a child must meet ADOS criteria and one of 3 “relaxed” ADI-R criteria. The relaxed ADI-R criteria are: 1) child meets the cutoff for the social domain AND is within 2 points of the cutoff for the communication domain, 2) child meets the cutoff for the communication domain AND is within 2 points of the cutoff of the social domain, or 3) child meets the cutoff for the social domain and is within 1 point of the cutoff for the behavioral domain. If a child meets any of these discordance criteria, he or she will be classified as an ASD case. More information on SEED final classifications can be found in Wiggins, Reynolds, Rice, et al. 2015.

2. Indeterminate ASD

The Indeterminate ASD group will include any child who is targeted for a full (POSSIBLE ASD) developmental evaluation but does not complete the ADOS or ADI-R or refuses testing with the ADOS or ADI-R (rendering final classification impossible). See Figures 6-8 for final classification diagrams.

Figure 6:

Final Classification for Children with a Previous ASD Diagnosis or Autism Exceptionality

3. DD with ASD Symptoms

[figure not shown]

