- Beyond genetic and geocode data, the composite SEED data files will contain up to 20,000 variables per participant for participant families. Although the major issues related to identifiability will be addressed, with this volume of data it is not possible to ensure that combination of data about a research participant will not result indirectly, by reference to other information to identification of study participants.

3. Study Analysis Categories and Basic Analytic Approaches

SEED will provide an unprecedented array of data on ASD cases and two comparison groups. Analyses can be crudely classified in the following categories: 1) characterization of phenotype (which includes case-only analyses and case-comparison group contrasts); 2) estimation of risk factor associations (includes evaluations of heritable and non-heritable risk factors, assessment of specificity of associations, and assessments of interactions); 3) comparison of biomarkers across ASD, DD, and POP groups; and 4) comparison of child health conditions across ASD, DD, and POP groups.

Recall that the final status of the ASD group subjects is based on the results of the children's developmental evaluation administered as part of the study data collection. In some instances, (e.g. refusal, loss to follow-up) these subjects may not complete the study's developmental evaluation and, thus, will be classified as Indeterminate ASD for analysis purposes. Consequently, analyses may be performed separately on subjects classified on the basis of the developmental evaluation and subjects classified on the basis of the ASD screen.

Both case-only analyses and case-comparison group contrasts will be conducted. Case-only analyses are primarily designed to identify novel, specific phenotypic subgroups in ASD, while the case-comparison group contrasts assess the specificity of an independent factor of interest with ASD – overall or by phenotypic subgroup – relative to the DD and POP. A priori, we may consider the following ASD subgroups for analysis:

- with (30%)/without (70%) regression
- with (40%)/without (60%) intellectual disability
- complex (20%)/essential (80%) autism
- verbal (70%)/nonverbal (30%)

These are not mutually exclusive categories, however, and one of our goals is to explore the utility of more complex combinations that include multiple features and may be potentially etiologically distinct, phenotypic subgroups.

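### The Indeterminate ASD rule treats one missing instrument as making classification impossible, but in two patterns the completed instrument already settles that the child is not a case

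*Protocol*

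**What the plan says.** **Case definition (Protocol III.E.1, Final ASD).** On the concordant route, a case is a child with a complete developmental evaluation who "meets the cutoff for autism on the ADI-R and ASD on the ADOS". For the ADI-R, "a child must have a social domain score" of at least 10, a communication score of at least 7 (nonverbal) or 8 (verbal), and a behavior score of at least 3. If the two instruments disagree, "a child must meet ADOS criteria and one of 3" relaxed ADI-R criteria:

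- "child meets the cutoff for the social domain AND is within 2 points of the cutoff for the communication domain"
- "child meets the cutoff for the communication domain AND is within 2 points of the cutoff of the social domain"
- social cutoff met, with behavior no more than 1 point short of its cutoff.

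**Missing instrument (III.E.2, Indeterminate ASD).** A child due for the full evaluation who does not complete, or refuses, the ADOS or the ADI-R is Indeterminate ASD. The reason given is "rendering final classification impossible". The text makes no exception for a completed instrument that has already excluded case status.

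**Non-cases (III.E.3 and III.E.5).** Children of ASD or DD origin who are tested and are not cases become DD with ASD symptoms. POP-origin children who have the full evaluation and are not cases stay in POP.

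**Analysis (III.K.3).** Subjects without a completed evaluation are Indeterminate ASD for analysis. Separate analyses may be done on subjects classified by the evaluation and on "subjects classified on the basis of the ASD screen".

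**The concern.** The reason given for the rule does not follow from the protocol's own case definition. When a necessary condition has been tested and failed, the other instrument cannot reverse it. Calling such a child unclassifiable discards information that the study has collected.

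Two consequences follow if the text is applied as written.

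- **POP.** This group is a random sample of the birth cohort (III.B.1, III.D.2). A POP-origin child reaches the full evaluation only if flagged by the SCQ, by a reported diagnosis or by behavior seen at the limited evaluation. Setting ruled-out children aside therefore removes members selectively, from the flagged end of the control group. Non-cases of ASD or DD origin are similarly lost from DD with ASD symptoms.
- **Screen-based analysis.** If the option in III.K.3 is used, a screen-positive child whom the study's own instrument has excluded could be counted as ASD. That sits badly with III.M, which relies on a stringent definition from standardized instruments to limit misclassification of cases.

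The patterns can plausibly occur. The ADI-R is a caregiver interview of about 120 minutes that can be held in clinic, at home or by telephone. The ADOS is a child observation of about 45 minutes. The 5.5-hour ASD visit may be split in two (III.H.6). Negative results need not be rare either: III.D.1 cites a study reporting SCQ specificity of 58% to 62% at the cutoff of 11.

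**Working it through.** No stated figure has to be reproduced. The check is whether case status can still change when one instrument is missing.

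**Inputs (III.E.1).** Let A mean that the ADOS cutoff is met. Let s, c and b be the ADI-R social, communication and behavior scores, and let C be the communication cutoff (7 nonverbal, 8 verbal).

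- Full ADI-R, F: s ≥ 10, c ≥ C and b ≥ 3.
- Relaxed 1, R1: s ≥ 10 and c ≥ C − 2 (5 nonverbal, 6 verbal).
- Relaxed 2, R2: c ≥ C and s ≥ 10 − 2 = 8.
- Relaxed 3, R3: s ≥ 10 and b ≥ 3 − 1 = 2.

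**Rule.** Case = A and (F or R1 or R2 or R3).

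**Step 1.** F implies R1, because s ≥ 10 and c ≥ C give c ≥ C − 2. A child failing R1, R2 and R3 has therefore failed F as well, and both routes are closed.

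**Step 2.** All three relaxed criteria fail in any of these situations:

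- s is below 8;
- s is below 10 and c is below C;
- s is at least 10, c is below C − 2 and b is below 2.

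**Step 3.** Let the missing instrument take every possible result.

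| Completed result | Missing | Possible outcomes |
|---|---|---|
| ADOS below cutoff | ADI-R | non-case only |
| ADI-R fails full and all relaxed criteria | ADOS | non-case only |
| ADOS met | ADI-R | case or non-case |
| ADI-R full criterion met | ADOS | case or non-case |
| ADI-R relaxed criterion only | ADOS | case or non-case |

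Enumerating scores over s 0-30, c 0-26 and b 0-12, verbal and nonverbal, gave this same table. Those score ranges are an assumption and do not affect the logic.

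**Result.** With one instrument missing, classification is truly open in three of the five patterns and closed in two. These are counts of logical patterns, not proportions of children. With both instruments missing, it is open.

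**The case against.** **The figures are not visible.** III.E says that final status is set out in Figures 6-8, and their notes place the definitions of untestable and refused testing in Figure 6. An exception may be there. This stands, and it is why the fix begins with checking the figures. The text itself states no exception.

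**The sentence can be read benignly.** The bracketed reason might restrict the rule to children for whom classification really is impossible, or the wording might mean that neither instrument was completed. III.K.3, which classes an uncompleted evaluation as Indeterminate, fits the either-missing reading better but does not settle it. Under the neither-completed reading, a child with one instrument would have no stated group, so the text would still need a sentence.

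**Requiring both instruments is a coherent convention.** It treats all partial completers alike, and the destinations in III.E.3 and III.E.5 are worded for tested or fully evaluated children. The point about destinations stands: non-case status follows from the case definition, but the final group has to be written in. The complete evaluation in III.E.1 is a condition for being a case. It does not leave non-case status unknown once a necessary criterion has failed.

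**The correction has its own bias.** Partial completers would be kept when negative and set aside when still compatible with ASD. This is true, and it calls for a repeat analysis.

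**Stronger readings that the protocol does not support.**

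- A reader might infer a count from Table 5, where 203 − 142 = 61 children per site, or 61 × 6 = 366 in all, enroll without completing. Table 5 starts from children presumed to have ASD and uses a 70% completion rate for the whole data collection protocol. It says nothing about how many have exactly one instrument, how many of those are negative, or how many come from POP.
- A reader might infer that Indeterminate children will count as cases in the main contrasts. III.K.3 makes the screen-based analysis optional and separate.
- A reader might treat every ruled-out child as a screen positive. A child who entered through a previous diagnosis with an SCQ below 11 is not one.

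**Conclusion.** The point holds on the text shown. The reason given in III.E.2 is untrue for two of the five patterns with one instrument missing: ADOS below cutoff with no ADI-R, and ADI-R failing the full and all relaxed criteria with no ADOS.

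The number of children affected cannot be derived from the protocol and may be small, because both instruments are normally part of the same evaluation. The effect on associations is likewise unquantified. In a screen-based analysis, any dilution of the case group could be modest, since III.E.3 describes DD with ASD symptoms as phenotypically closer to ASD than other DD.

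The change is worth making because group assignment underlies every ASD, DD and POP contrast, the loss from POP is selective, and the data needed are already collected. The conclusion assumes that III.E.2 applies when either instrument is missing and that Figures 6-8 contain no exception.

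**What to change.** 1. Check Figures 6-8, including the definitions of untestable and refused testing. If they already make the exception, bring III.E.2 into line with them. If not, amend both.
2. Limit Indeterminate ASD to children with neither instrument completed, or whose one completed instrument is still compatible with Final ASD.
3. Record the two ruled-out patterns as non-cases by group of origin: DD with ASD symptoms for ASD or DD origin, POP for POP origin. State this explicitly, because III.E.3 and III.E.5 do not cover partly evaluated children.
4. State that these children do not count as ASD in any screen-based analysis under III.K.3.
5. Apply the same derivation to the pooled SEED 1 and 2 data where possible, so that the groups mean the same across phases.
6. Report how many children fall in each pattern by group of origin, and repeat the main contrasts without the ruled-out partial completers.

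The cost is a change in the classification program, a few sentences of text, any needed correction to the figures and one repeat analysis. No new data collection is needed. The downside is that partial completers are then retained only among non-cases; item 6 shows whether this matters.
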